1 INTRODUCTION

The purpose of this statistical analysis plan (SAP) is to provide details of the statistical analyses that have been outlined within Protocol Amendment 6 for Study ACE-LY-004, which is entitled "An Open-label, Phase 2 Study of ACP-196 in Subjects with Mantle Cell Lymphoma" dated 19 July 2016. Any changes to the methods described in the final SAP will be documented in the clinical study report (CSR). Hereafter, acalabrutinib (a generic name for ACP-196) will be used in place of ACP-196 in this document.

Separate reports will be generated for pharmacokinetic (PK) and pharmacodynamic data.

2 OBJECTIVES

2.1 Primary Objectives

To determine the activity of acalabrutinib in subjects with relapsed/refractory
(R/R) mantle cell lymphoma (MCL) as measured primarily by response rate. In
addition, activity of acalabrutinib will be assessed by duration of response (DOR),
progression-free survival (PFS), and overall survival (OS).

2.2 Secondary Objectives

- To characterize the safety profile of acalabrutinib
- To characterize the PK profile of acalabrutinib
- To evaluate the PD effects of acalabrutinib

3 STUDY OVERVIEW

3.1 Study Design

This clinical trial is a phase 2, multicenter (approximately 70 global centers), open-label study in subjects with histologically documented MCL, who have relapsed after or were refractory to ≥1 (but not >5) prior treatment regimens. Subjects will be enrolled and will take 100 mg of acalabrutinib twice per day (bid) in repeated 28-day cycles.

Treatment with acalabrutinib may be continued until disease progression or an unacceptable drug-related toxicity, whichever occurs first. Dose modification provisions are provided in the study protocol. All subjects who discontinue study drug will have a safety follow-up visit 30 (+7) days after the last dose of acalabrutinib. An early

Acerta Pharma Confidential Page 6 of 28

termination visit is required for any subjects who permanently discontinued study drug for any reason including disease progression (exceptions included death, lost to followup, or withdrawal of consent).

All subjects will have hematology, chemistry, and urinalysis safety panels done at screening. Once dosing commences (Day 1), all subjects will be evaluated for safety, including serum chemistry and hematology, once weekly for the first 4 weeks, every 2 weeks in Cycle 2, every 4 weeks in Cycles 3 to 12, and every 12 weeks thereafter. PK/PD testing will be done in Cycles 1 and 2. Tumor assessments will be completed at 8- to 12-week intervals during the trial.

The primary efficacy analyses will be based on investigator assessment. An Independent Review Committee (IRC) will assess the efficacy endpoints in accordance with the IRC charter provided separately from this document.

3.2 Sample Size

The study will enroll approximately 117 subjects.

A one-sample Chi-square test with a 0.025 1-sided significance level will have more than 99% power to test the null hypothesis that overall response rate (ORR) will be \leq 20% (not considered clinically compelling) versus the alternative hypothesis that ORR will be \geq 40%. The sample size will also provide adequate estimation utility for safety and other secondary analyses. In particular with a sample size of 117 subjects, the probability of observing 1 or more instances of a specific adverse event (AE) with a true incidence rate of 1%, 2% or 5% is 69.1%, 90.6%, or 99.8%, respectively. This provides reasonable assurance that events occurring at \geq 1% frequency can be identified in this Phase 2 study.

EAST6 (Version 6.3.1) was employed to conduct the sample size calculation.

4 STUDY ENDPOINTS

4.1 Primary Endpoints

The primary endpoint of the study is the ORR, defined as the proportion of subjects achieving either a partial response (PR) or complete response (CR) per the Lugano classification for non-Hodgkin lymphoma (NHL) (Cheson 2014) (hereafter referred to as Lugano classification) as assessed by investigators.

Acerta Pharma Confidential Page 7 of 28

FDA provided the feedback that ORR by IRC should be used as primary endpoint for labeling purposes via Type C Content and Format meeting for the MCL New Drug Application (NDA). Since the study was conducted with investigator assessed ORR per Lugano classification as the primary endpoint, the SAP will retain the investigator primary to be consistent with the protocol. To meet labeling needs, both IRC and investigator assessed ORR will be analyzed in the same fashion, i.e., all planned analyses for the investigator assessed ORR will also be provided for the IRC assessed ORR per Lugano classification.

4.2 Secondary Endpoints

4.2.1 Efficacy

- DOR per Lugano classification as assessed by investigators
- PFS per Lugano classification as assessed by investigators
- OS
- IRC-assessed ORR, DOR, and PFS per Lugano classification

4.2.2 Safety

- Frequency and severity of AEs/SAEs
- Frequency of AEs requiring discontinuation of study drug or dose reductions
- Effect of acalabrutinib on peripheral T/B/natural killer (NK) cell counts
- Effect of acalabrutinib on serum immunoglobulin levels

4.2.3 Pharmacokinetics

Plasma pharmacokinetics of acalabrutinib

4.3 Exploratory Endpoints

Acerta Pharma Confidential Page 8 of 28

5 HYPOTHESES AND MULTIPLICITY

No formal statistical hypotheses will be tested. The clinical hypotheses are that acalabrutinib monotherapy is safe and effective in subjects with R/R MCL.

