Statistical Methods:	
Approximately 117 subjects meeting the stated eligibility requirements will be enrolled onto the study.
 
A one-sample Chi-square test with a 0.025 1-sided significance level will have more than 99% power to test the null hypothesis that ORR will be $\leq 20\%$ (not considered clinically compelling) versus the alternative hypothesis that ORR will be $\geq 40\%$. The sample size will provide adequate estimation utility for safety and other secondary analyses. In particular, with a sample size of 117 subjects, the probability of observing 1 or more instances of a specific AE with a true incidence rate of 1%, 2% or 5% is 69.1%, 90.6% or 99.8%, respectively. This provides reasonable assurance that events that occurring at $\geq 1\%$ frequency can be identified in this Phase 2 study.
 
The final analysis of primary and secondary efficacy endpoints will occur approximately 14 months after the last subject has been enrolled.
 
A follow-up analysis will be performed 24 months after the last subject has been enrolled, and close-out analysis will be performed approximately 54 months after enrollment of the last subject.

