1.5.2 Clinical Experience

Acerta Pharma is developing acalabrutinib for the treatment of patients with cancer or autoimmune disorders. The safety data of acalabrutinib monotherapy are consistent among studies. Preliminary data as of 01 June 2016, based on 134 subjects with relapsed and refractory CLL, have been evaluated for tumor response based on International Working Group response criteria ([Hallek 2008](#)) as updated ([Cheson 2012](#)) to include PR with treatment-induced lymphocytosis (PRL). With a median follow up of 15.5 months, an ORR of 96.9% has been observed. Preliminary data through 01 June 2016 are also available on the first 99 sequentially enrolled subjects with previously untreated CLL. With a median follow up of 14.8 months, the ORR is 97.9% in subjects with previously untreated CLL. Overall in the ACE-CL-001 relapsed and refractory and treatment-naive cohorts, as of the 01 June 2016 data cut-off date, few subjects have experienced disease progression.

Preliminary data through 01 June 2016 are also available on the first 124 sequentially enrolled subjects with relapsed/refractory MCL who were treated with acalabrutinib on this protocol (ACE-LY-004). With a median follow up of 6.9 months, the ORR is 80.6%, with CR in 31.5% of subjects.

For detailed information on acalabrutinib clinical experience, refer to the Acalabrutinib IB.

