5.2 SAMPLE SIZE CONSIDERATIONS

The study will enroll approximately 117 subjects.

A one-sample Chi-square test with a 0.025 1-sided significance level will have more than 99% power to test the null hypothesis that ORR will be $\leq 20\%$ (not considered clinically compelling) versus the alternative hypothesis that ORR will be $\geq 40\%$. The sample size will also provide adequate estimation utility for safety and other secondary analyses. In particular, with a sample size of 117 subjects, the probability of observing 1 or more instances of a specific AE with a true incidence rate of 1%, 2%, or 5% is 69.1%, 90.6%, or 99.8%, respectively. This provides reasonable assurance that events that occurring at $\geq 1\%$ frequency can be identified in this Phase 2 study.

EAST6 (Version 6.3.1) was employed to conduct the sample size calculation.

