5.5.3 Analysis of Efficacy Parameters

Primary Efficacy Endpoint

The primary efficacy endpoint is the ORR as assessed by investigators. The ORR is defined as the proportion of subjects achieving either a PR or CR, according to the Lugano Classification for NHL ([Cheson 2014](#)), as assessed by investigators. The corresponding 95% two-sided confidence interval will be derived.

Secondary Efficacy Endpoints

Duration of Response

The DOR is defined as the interval from the first documentation of CR or PR to the earlier of the first documentation of objective MCL disease progression or death from any cause. Kaplan-Meier methods will be used to estimate event-free curves and corresponding quantiles (including the median).

Progression-free Survival

PFS is defined as the interval from the start of acalabrutinib therapy to the earlier of the first documentation of objective MCL disease progression per investigator assessment or death from any cause. Kaplan-Meier methods will be used to estimate the event-free curves and corresponding quantiles (including the median).

Overall Survival

The duration of OS will be measured from the time of first study drug administration until the date of death. Subjects who are known to be alive as of their last known status will be censored at their last date known to be alive. Kaplan-Meier methodology will be used to estimate overall survival curves and corresponding quantiles (including the median).

IRC-assessed Endpoints per Lugano Classification

ORR, DOR, and PFS assessed by the IRC per Lugano Classification will be analyzed using the same analysis methods described for investigator-assessed endpoints. The discordant responses assessed by the investigator and IRC using Lugano Classification will be provided.

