10.6.1.2 Analysis Methods

The primary analysis of ORR will be conducted on the All-treated Population. ORR and the corresponding 95% two-sided CI calculated using the exact binomial distribution will be presented. Subgroup analysis per Section 6.2 will be provided.

The order of overall response category is: CR > PR > SD > PD. Descriptive statistics will be provided for best overall response. The number and proportion of subjects within each category of response as well as the associated 95% Cls will be presented. The proportion will be estimated by dividing the number of subjects within each category of response by the total number of subjects in the analysis population. Each subject will be counted within only one response group, with the best response during the study as the classification group.

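### Does it matter that the sample size rests on a test of ORR ≤20% when SAP Section 5 says nothing will be tested?

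*SAP*

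**What the plan says.** **Sample size.** Protocol Section 5.2 states: "A one-sample Chi-square test with a 0.025 1-sided significance level will have more than 99% power to test the null hypothesis" that ORR is at most 20%, against an alternative of at least 40%. The Synopsis and SAP Section 3.2 say the same. All three describe 20% as a rate that would not be clinically compelling. Protocol Section 5.2 and SAP Section 3.2 name EAST6 as the software used.

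**Hypotheses.** SAP Section 5 reads: "No formal statistical hypotheses will be tested". It adds only a clinical hypothesis, without a threshold, that the drug is safe and effective.

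**Primary analysis.** Protocol Section 5.5.3 says of ORR: "The corresponding 95% two-sided confidence interval will be derived". SAP Section 10.6.1.2 specifies the method: "95% two-sided CI calculated using the exact binomial distribution will be presented". SAP Section 10.1 describes efficacy summaries as descriptive. None of these sections compares the interval with 20% or calls for a p-value.

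**Assessor.** SAP Section 4.1 keeps investigator-assessed ORR as primary and says that "both IRC and investigator assessed ORR will be analyzed in the same fashion".

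**Origin of 117.** SAP Section 7 explains that two parallel Simon two-stage cohorts were merged and that 117 was kept so that enough safety and exposure data would be collected. The response cut-offs given there (at least 8 of 28 and at least 3 of 12) were rules for continuing at a completed futility interim. They are not criteria for the final analysis.

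**The concern.** Power is a property of a test. If no test is done, a power above 99% describes nothing the trial will carry out; if one is done, SAP Section 5 is wrong. SAP Section 11 reports no major change from the protocol's analyses, so the SAP does not address the mismatch.

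The obvious inference, that success means an interval lying above 20%, is not quite the test named in the sample size text. Without a continuity correction, the chi-square test rejects at a count where the exact interval still includes 20%. In a trial with a result near 20%, an unstated rule would let the more favourable reading be chosen afterwards. The point gains some weight from SAP Section 4.1, which records that the FDA asked for IRC-assessed ORR as the primary endpoint for labeling.

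**Working it through.** **Inputs.** n = 117, null 20%, alternative 40%, one-sided 0.025 (Protocol 5.2, SAP 3.2); exact two-sided 95% interval (SAP 10.6.1.2); 80.6% of 124 subjects (Protocol 1.5.2).

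**1. The plan's power figure.** Normal approximation with the null variance:

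- Standard error under the null: √(0.2 × 0.8 / 117) = 0.03698
- Standard error under the alternative: √(0.4 × 0.6 / 117) = 0.04529
- Power = Φ[(0.40 − 0.20 − 1.96 × 0.03698) / 0.04529] = Φ(2.816) = 0.9976

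Other versions give 0.9930 (alternative variance), 0.9967 (continuity-corrected) and 0.9971 (exact binomial). The claim of more than 99% holds in every version.

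**2. Where each possible rule would cut.** The uncorrected statistic is z = (x/n − 0.2) / √(0.16/n), and the chi-square rule takes the smallest x with z > 1.96. The interval rule takes the smallest x whose exact (Clopper-Pearson) lower limit exceeds 20%. The error is the exact binomial P(X ≥ x) at a true ORR of 20%.

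| n | Rule | Responders needed | Exact one-sided error | Exact lower limit at that count |
|---|---|---|---|---|
| 117 | Chi-square, uncorrected | 32 (27.4%; z = 1.99) | 0.034 | 19.5% |
| 117 | Exact 95% interval above 20% | 33 (28.2%) | 0.021 | 20.3% |
| 124 | Chi-square, uncorrected | 34 | 0.029 | 19.8% |
| 124 | Exact 95% interval above 20% | 35 | 0.018 | 20.5% |

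With a continuity correction the chi-square cut-off at n = 117 is also 33: (32 − 0.5 − 23.4)/4.327 = 1.87 falls short of 1.96, and (33 − 0.5 − 23.4)/4.327 = 2.10 passes. Here 23.4 = 117 × 0.2 and 4.327 = √(117 × 0.16). At n = 124 the corrected cut-off is 35, again the same as the interval rule.

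**3. Does the planned interval deliver the stated error and power?** The documents say approximately 117, so take 110 to 130 treated subjects as an assumed range. Reading the exact interval against 20% gives a one-sided error of 0.016 to 0.025 (never above 0.025) and power at 40% of at least 99.5% throughout. The uncorrected chi-square test exceeds 0.025 at 15 of those 21 sizes. The method the SAP does plan is therefore the one that honours the 0.025.

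**4. Distance from the threshold.** Protocol Section 1.5.2 reports that "the ORR is 80.6%, with CR in 31.5% of subjects" among the first 124 enrolled. 0.806 × 124 = 99.9, taken as 100 responders; the exact 95% interval is 72.6% to 87.2%. To miss the interval rule at n = 124 the count would have to be 34 or fewer, which means losing 100 − 34 = 66 of those 100 responders.

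**The case for a change.** The best opposing argument is about pre-specification rather than this trial's result. A plan may size on a notional test and then estimate, but it should say so, and these documents do not. Two assessors and a labeling use make an explicit criterion more desirable, and one sentence would supply it at no cost in patients or data.

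Part of this stands: no sentence links SAP Section 3.2 to SAP Section 5, and no success rule is written. The stronger claim, that the two sections give opposite answers, does not stand. Section 3.2 says what power a test would have, not that the test will be run. Section 5 answers that question directly, and Sections 10.1 and 10.6.1.2 agree with it. SAP Section 7 also shows that 117 was carried over from the previous design, so the power statement describes a sample size already fixed.

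Nor is the obvious repair clearly better. A formal rejection rule added now would put a test into a SAP that disclaims one, after open-label results far above 20% were known, and so would have no confirmatory value. Relabelling the sample size calculation as exact binomial would misdescribe a calculation that the documents report as a chi-square calculation in EAST6.

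**Conclusion.** No change follows. Carried out exactly as written, the plan yields ORR with a valid exact 95% interval for both the investigator and IRC assessments. A reader can set its lower limit beside the 20% that the documents themselves treat as uninteresting. A two-sided 95% interval matches the one-sided 0.025 level used for planning, so this comparison needs nothing the plan lacks.

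The gap is a missing linking sentence that analysts will fill sensibly. The most it could affect is one responder at 117 or 124 subjects, and only if someone used a chi-square test that the SAP does not plan. Against a preliminary count of about 100 of 124, with cut-offs of 34 or 35, one responder is immaterial.

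This rests on three assumptions: that 80.6% of 124 means 100 responders; that the final investigator and IRC rates are not drastically below that preliminary figure, for which Section 1.5.2 does not name the assessor; and that the number treated lies within about 110 to 130.

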6 ANALYSIS SUBSETS

6.1 All-treated Population

The safety analyses and primary efficacy analyses for all efficacy endpoints will be performed on the All-treated Population, defined as all enrolled subjects who receive ≥1 dose of study drug. The analyses of DOR and of the All-treated Population who achieve CR or PR as their best overall response.

6.2 Subgroup Analysis

Subgroup analysis will be performed for ORR and CR per Lugano classification as assessed by investigators using the following baseline variables:

- Age (<65 years versus ≥65 years; <75 years versus ≥75 years)
- Sex (male versus female)
- Race (White versus non-White)
- Ann Arbor staging for lymphoma (1-3 versus 4)
- Simplified MCL international prognostic index (MIPI) (low risk [0 to 3] versus intermediate risk [4 to 5] versus high risk [6 to 11])
- Eastern Cooperative Oncology Group (ECOG) performance status (0 versus 1 versus ≥2)
- Bone marrow involvement (yes/no)
- Extranodal disease (yes/no)
- Tumor bulk (largest diameter) (<5 cm versus ≥5 and <10 cm versus ≥10 cm)
- Refractory disease (yes/no)

- Gastrointestinal disease (yes/no)
- Prior number of regimens (1 versus 2 versus ≥3)
- Prior proteasome inhibitor (yes/no)
- Prior stem cell transplant (yes/no)
- Prior hyper CVAD regimen: cyclophosphamide, vincristine, doxorubicin, dexamethasone (yes/no)
- Prior lenalidomide (yes/no)
- Region (United States [US] versus Ex-US)

7 INTERIM ANALYSIS AND EARLY STOPPING GUIDELINES

Prior to Protocol Amendment 4.0, dated 14 November 2015, the protocol consisted of 2 parallel cohorts (bortezomib-naive and the bortezomib-exposed) each based on a Simon's 2 stage design. Subjects who received at least two cycles of other commercially available proteasome inhibitors (eg. carfilzomib) were enrolled into the bortezomib-exposed cohort.

An interim analysis for futility based on response rate was performed in September 2015 per Protocol Amendment 3 (dated 17 July 2015). In this interim analysis, within the first 28 patients enrolled to bortezomib-naive cohort, the required response rate for continuation (≥8/28 responders) was exceeded. Within the first 12 subjects enrolled to the bortezomib-exposed cohort, the required response rate for continuation (≥3/12 responders) was also exceeded. Based on this interim analysis, enrollment to both study cohorts could continue without interruption.

The protocol was amended in November 2015 (Protocol Amendment 4.0) based on emerging data that support the merging of the 2 cohorts by prior bortezomib exposure. The Phase 2 study of ibrutinib in R/R MCL reported similar overall response rates in the bortezomib-naive and bortezomib-exposed subjects (68% and 67%, respectively) (Wang 2013), indicating that prior bortezomib exposure does not appear to influence response to Btk inhibitor therapy. This is further supported by emerging data from this study (ACE-LY-004). The study will retain the original planned sample size of 117 subjects to obtain adequate safety and exposure data with acalabrutinib in this patient population.

The futility analysis is not expected to have any meaningful impact on the final analysis of this study; therefore, no adjustment will be made.

Acerta Pharma Confidential Page 10 of 28

Statistical Analysis Plan

8 FINAL ANALYSIS AND CLINICAL STUDY REPORT

The final analysis of primary and secondary efficacy endpoints will occur approximately 14 months after the last subject has been enrolled. A follow-up analysis will be performed when all subjects have completed their study participation. The CSR will be written based on the final analysis and the CSR addendum will be written at the time of follow-up analysis.

9 MISSING VALUES

9.1 Safety Data

Imputation of partial dates will be made for AE onset and stop dates, start and end dates of concomitant medication, start date of subsequent anticancer therapy, date of initial diagnosis and death date. If dates are completely missing, no imputation will be made. For any partial date with missing year, no imputation will be made.

The general rule for imputation is:

- If only day is missing, then the 15th of the month will be used.
- If only year is present, then June 30th will be used.

If such imputation date for initial diagnosis is on or after date of first dose, the date of first dose -1 will be used. If such imputed date for subsequent anticancer therapies is before the date of last dose, the date of last dose +1 will be used.

If the imputed date is for an AE start date and is in the same year and month as the first dose date but before the first dose date, then the first dose date will be used, or if the imputed AE start date is after the AE end date, then the AE end date will be used. If the imputed date is for an AE start date and is in the same year and month as but after the last dose date + 30 days, then the last dose date + 30 days will be used.

If the imputed date is for an AE end date and is after the death date, the date of death will be used, or if the imputed AE end date is before the AE start date, the AE start date will be used.

Acerta Pharma Confidential Page 11 of 28

Statistical Analysis Plan

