4.2 INVESTIGATOR'S ASSESSMENT OF RESPONSE TO TREATMENT

The investigator must rate the response of the subject's MCL to treatment consistent with clinical guidelines ([Cheson 2014](#)) as listed in [Table 4-2](#).

Overall response assessments will include evaluation of physical exams, bone marrow assessments, and radiographic evaluations per the Schedule of Assessments ([Appendix 4](#)). Subjects who have signs and symptoms of progression outside of the scheduled assessment should be evaluated by the investigator with a physical exam and laboratory assessments to determine if disease progression is present. Any suspected case of disease progression should be confirmed with a CT and/or PET/CT scan, if one was not obtained, and should be reported to the sponsor or designee. It is

recommended that disease progression identified by PET/CT alone be confirmed by an alternative imaging modality (eg, diagnostic quality CT) or by biopsy. Subjects may continue study treatment until progression is confirmed by a serial exam at least 2 weeks later. In addition, when clinically appropriate, based on investigator-perceived risk/benefit assessment, a subject may continue treatment until objective progression is confirmed. New anticancer therapy should be withheld if clinically appropriate in the absence of objectively confirmed progressive disease.

Table 4-2. Response Assessment Criteria for MCL (Cheson 2014)

Response and Site	PET-CT-Based Response	CT-Based Response
Complete	Complete metabolic response	Complete radiologic response (all of the following)
Lymph nodes and extra lymphatic sites	Score 1, 2, or 3* with or without a residual mass on 5PS† It is recognized that in Waldeyer’s ring or extranodal sites with high physiologic uptake or with activation within spleen or marrow (eg, with chemotherapy or myeloid colony-stimulating factors), uptake may be greater than normal mediastinum and/or liver. In this circumstance, complete metabolic response may be inferred if uptake at sites of initial involvement is no greater than surrounding normal tissue even if the tissue has high physiologic uptake	Target nodes/nodal masses must regress to ≤1.5 cm in LDi No extralymphatic sites of disease
Nonmeasured lesion	Not applicable	Absent
Organ enlargement	Not applicable	Regress to normal
New lesions	None	None
Bone marrow	No evidence of FDG-avid disease in the marrow	Normal by morphology; if indeterminate, IHC negative

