9.2 Efficacy Data

The method for handling missing data is described in the definition for each of the efficacy endpoints. Every effort will be made to obtain complete dates for deaths. In the event of a partial or missing death date, the algorithm in Appendix13.2 will be used.

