10.5.3 Subsequent Anticancer Therapy for MCL

Subsequent anticancer treatments for MCL are reported on the alternative cancer therapy CRF. Treatment started after discontinuation of acalabrutinib (i.e. started after the last dose of acalabrutinib) will be considered as subsequent anticancer treatment for MCL. The start date of first subsequent anticancer treatment will be considered as the start of subsequent anticancer therapy. Subject listing of subsequent anticancer therapy for MCL will be provided.

Acerta Pharma Confidential Page 14 of 28

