13.4 Censoring Rules for Progression-free Survival

13.4.1 Primary Analysis of PFS

Situation	Outcome	Date	Event Description/ Censoring Reason
Progression documented between scheduled visits on or before receiving subsequent anticancer therapy or data cutoff, whichever occurred first	Event	Earliest date of disease assessment documenting progression	PD
Death without documented PD and not receiving subsequent anticancer therapy on or before data cutoff	Event	Date of Death	Death
Documented PD or death after subsequent anticancer therapy and the subsequent anticancer started before data cutoff date	Censored	Date of last adequate disease assessment prior to subsequent anticancer treatment	Subsequent anticancer therapy
No documented PD or death at the time of data cutoff and subsequent anticancer therapy started before the data cutoff	Censored	Date of last adequate disease assessment prior to subsequent anticancer treatment	Subsequent anticancer therapy
Documented PD or death after subsequent anticancer therapy and the subsequent anticancer started after data cutoff date	Censored	Date of last adequate disease assessment on or before data cutoff	Data cutoff
No documented PD or death at the time of data cutoff and subject not received subsequent anticancer therapy or subsequent anticancer therapy started after the data cutoff	Censored	Date of last adequate disease assessment on or before data cutoff	Data cutoff
Withdrew consent without documented PD or death	Censored	Date of last adequate disease assessment	Withdrew consent
Lost to follow-up without documented PD or death	Censored	Date of last adequate disease assessment	Lost to follow-up
No post-baseline adequate disease assessments	Censored	Date of first dose	No postbaseline adequate disease assessments
No baseline disease assessments	Censored	Date of first dose	No baseline disease assessment

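### SAP 9.1 can place a partially dated start of subsequent therapy before a documented progression that came first, so DOR and primary PFS censor a real event

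*SAP*

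**What the plan says.** SAP 9.1 (Safety Data) includes among the dates to be imputed the "start date of subsequent anticancer therapy, date of initial diagnosis and death date". The rules are "If only day is missing, then the 15th of the month will be used" and "If only year is present, then June 30th will be used". For subsequent therapy the one further condition is "If such imputed date for subsequent anticancer therapies is before the date of last dose, the date of last dose +1 will be used".

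SAP 9.2 (Efficacy Data) states that "The method for handling missing data is described in the definition for each of the efficacy endpoints". Those definitions, and the censoring appendices they point to, give no separate rule for a partial therapy start. SAP 10.5.3 adds: "The start date of first subsequent anticancer treatment will be considered as the start of subsequent anticancer therapy".

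SAP 13.3 (DOR) and 13.4.1 (primary PFS) share the same rows. A PD on or before the start of subsequent therapy is an event. The row "Documented PD or death after subsequent anticancer therapy and the subsequent anticancer started before data cutoff date" is censored at the last adequate assessment before that therapy. SAP 13.4.2 gives a PFS sensitivity analysis in which every PD or death is an event, whatever the therapy date. No counterpart is given for DOR.

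Protocol 4.2 describes the intended order: "New anticancer therapy should be withheld if clinically appropriate in the absence of objectively confirmed progressive disease".

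**The concern.** The imputed therapy date acts as a switch between event and censoring, but it is bounded by the last dose and not by the PD it is compared with. Other partial dates in the SAP are reconciled with the dates that matter to them: AE starts with first dose, AE end and last dose + 30 days; AE ends with AE start and death; diagnosis with first dose; death with last contact (SAP 9.1 and 13.2).

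The situation is foreseeable. Subjects who stop drug for reasons other than progression are scanned about every 24 weeks afterwards (Protocol 4.4), and drug may be held for up to 28 days (Protocol 3.5.5), so PD can be documented after the last dose. Later therapy is ascertained about every 24 weeks by visit or telephone (Protocol 4.4), which makes partial dates plausible.

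At stake are DOR and primary PFS, both secondary endpoints. A PD that came first would be removed as an event, and follow-up cut back to an earlier scan.

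**Working it through.** The documents give no figure for this, so the check applies the rule as written.

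**Rule.** Imputed start = the 15th of the known month, or June 30 of the known year; if that is before the last dose, use last dose + 1. PD is an event if PD date ≤ imputed start; otherwise it is censored.

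**Worked cases** (true order: last dose, PD, new therapy)

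| Last dose | PD | True start, as recorded | Imputed start | Result |
|---|---|---|---|---|
| 2 Sep | 20 Sep | 26 Sep, day missing | 15 Sep | PD censored |
| 18 Sep | 22 Sep | 26 Sep, day missing | 19 Sep (floor) | PD censored |
| 20 May | 10 Aug | 25 Aug, year only | 30 Jun | PD censored |
| 22 Sep | 22 Sep | 26 Sep, day missing | 23 Sep (floor) | PD is an event |

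If the previous scan was 84 days before PD (an assumption: 12 weeks, the upper end of the interval in SAP 3.1), each censored case loses 84 days.

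**Share misordered, fixed gap.** Let therapy start H days after PD, with PD at least 7 days after the last dose. Count all true start days s in a 30-day month. The PD is lost when s − H > 15, which is max(0, 15 − H) of 30 days. For year-only dates June 30 is day 181, so the PD is lost when s − H > 181, which is (184 − H) of 365 days.

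| H (days) | Day missing | Year only |
|---|---|---|
| 0 | 15/30 = 50% | 184/365 = 50% |
| 3 | 12/30 = 40% | 181/365 = 50% |
| 7 | 8/30 = 27% | 177/365 = 48% |
| 14 | 1/30 = 3% | 170/365 = 47% |
| 28 | 0/30 = 0% | 156/365 = 43% |

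The floor changes nothing here, because last dose + 1 is still before PD. If PD is on the last-dose date the share is 0%. If PD is one day later it is at most 1/30, arising when the imputed date equals the last-dose date, which the rule does not move.

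**Share misordered, exponential gap of mean m, PD day uniform.**

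- Day missing: 0.5 − (m/30)(1 − e^(−15/m)). For m = 7: 0.5 − 0.233 × 0.883 = 29%. For m = 14: 0.5 − 0.467 × 0.657 = 19%. For m = 28: 0.5 − 0.933 × 0.415 = 11%.
- Year only: 184/365 − (m/365)(1 − e^(−184/m)). For m = 14: 0.504 − 0.038 = 47%. For m = 60: 0.504 − 0.157 = 35%.

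The day-missing result therefore depends heavily on the assumed gap distribution; the year-only result much less so.

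**Reverse order.** Let therapy truly start H days before PD, with the last dose 7 days before that start. The imputed start falls on or after PD when s ≤ 15 − H: 12/30, 8/30 and 1/30 start days for H = 3, 7 and 14. A PD that the plan would censor then becomes an event.

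**Time lost.** With the day missing, about one assessment interval: 8-12 weeks per SAP 3.1, about 24 weeks under the later protocol (4.1.20 and 4.4). It can be longer for year-only dates, where several scans may lie between June 30 and PD.

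**The case against.** The usual path is protected. Treatment runs until progression (Protocol 3.1), and subjects may stay on drug until PD is confirmed at least 2 weeks later (Protocol 4.2). The last dose then falls on or after the first PD date, and the floor keeps the event. The problem needs a PD after the last dose, a partial therapy date and an unfavourable calendar position together. This stands, and it limits the number of subjects.

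For PFS, the sensitivity analysis in SAP 13.4.2 ignores the therapy date and would show any effect. This also stands, but that is not the primary PFS analysis, and DOR has no equivalent.

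Section 9.1 is headed as safety data, so using it for efficacy censoring is an inference. That is fair, but no other rule for this date is given.

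A reader might infer that the error runs one way and inflates PFS and DOR. The documents do not support that. It holds only when PD came first. The withholding instruction in Protocol 4.2 is conditional on clinical appropriateness, Protocol 4.4 provides for alternative therapy before progression, and 4.1.22 continues follow-up to progression regardless of later therapy. Both orders can occur, and their mix is unknown.

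Finally, a bound at PD is itself one-sided: it counts some PDs that truly followed therapy as events. That cost is real and is sized under the fix.

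**Conclusion.** The concern holds as a conditional defect in a stated rule. Followed exactly, the SAP can censor a PD that preceded new therapy, in both DOR and primary PFS, when PD is documented about 2 or more days after the last dose and the therapy start is partial. Conditional on that situation and on PD having come first, the misordered share is about 0-30% with the day missing, for gaps of 7-28 days, and roughly 35-50% with only the year known. These figures rest on assumed gaps and a uniform calendar position.

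They are not shares of the trial's events. The documents give no count of partial therapy dates, and the number affected is probably small. The net direction of bias is not known. ORR has no therapy-date censoring rule and is unaffected.

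**What to change.** Add to SAP 9.1, for DOR and PFS: if the known month (or, where only the year is known, the year) of the subsequent-therapy start is that of a documented PD, the imputed start may not be earlier than the PD date, unless the record shows that therapy began before PD. The PD date itself is enough, because a PD on the day therapy starts is already an event. A PD in an earlier month or year than the therapy start needs no new rule, since the imputed date already falls after it. Enumeration over gaps of 0-59 days from last dose to PD and 0-39 days from PD to therapy left no wrongly censored PD.

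List every subject with an imputed therapy start, and add for DOR the analysis that 13.4.2 gives for PFS (every PD or death an event).

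The cost is a few sentences in the SAP, one programming condition, one listing and one extra DOR run. The statistical cost falls on subjects whose therapy truly began first when the record does not show it. With an exponential gap of mean m and the last-dose floor not triggered, the share of such PDs counted as events becomes 1 − (m/D)(1 − e^(−D/m)):

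- Day missing, D = 30, m = 14: from about 19% to 1 − 0.467 × 0.883 = 59%.
- Year only, D = 365, m = 60: from about 34% to 1 − 0.164 × 0.998 = 84%.

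This adds events and so is conservative for a single-arm estimate of DOR or PFS. The listing lets readers see how many cases are involved.
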